3.2 DISCUSSION OF TRIAL DESIGN, INCLUDING THE CHOICE OF CONTROL GROUP(S)

This is a 14-week, open-label, randomized, single dose, parallel arm trial to investigate and compare the PK, safety, tolerability and immunogenicity of BI 695501 administered subcutaneously in the thigh via prefilled syringe or autoinjector.

Due to the long half-life of BI 695501, a parallel group design was selected, with administration of BI 695501 as a single dose only. Additionally, randomization minimizes selection bias between the treatment groups.

Blinding is not possible because the BI 695501 presentations are visually distinguishable. The open-label treatment is not expected to bias the PK results, since the trial endpoints are derived from measurement of plasma concentrations of the analyte provided by a bioanalytical laboratory which is blinded to treatment allocation.

It is not expected that the device itself, being a prefilled syringe or an autoinjector, has an influence on the bioavailability in terms of rate and extent of absorption especially considering the long half-life of the compound. The most likely important variable is the reliability of the injection with regards the depth of the injection and thus the tissue reached as well as the amount of drug being injected by the device. The injection characteristics are

more likely influenced by the amount of s.c. fat tissue. Body mass index and weight have a good correlation with s.c. fat tissue thus the inclusion of healthy subjects having a broad range of weight would give a better estimation of the reliability and performance of the devices.

The group size of up to 80 subjects per treatment group is considered adequate for an evaluation of the PK, safety, tolerability, and immunogenicity for the primary analysis report to support the primary objective of the study.

3.3 SELECTION OF TRIAL POPULATION

It is planned that in total up to 160 healthy male and female subjects will enter the trial. All efforts will be made to enroll in all 3 weight categories, in order to ensure a wide distribution of weight in the study.

Subjects, who prematurely discontinue the trial due to any reason, may be replaced to ensure sufficient numbers complete the trial. Thus the planned number of subjects entered may exceed a total of 160. They will be recruited from the volunteers' pool of the trial sites.

Male and female healthy subjects with a weight in the indicated weight groups will be included into the trial. This will ensure that performance of the devices is tested in a wide range of weight ranges and is representative of wider patient population.

A log of all subjects enrolled into the trial (i.e. who have signed informed consent) will be maintained in the ISF at the investigational site irrespective of whether they have been treated with investigational drug or not.

3.3.1 Main diagnosis for trial entry

The trial will be performed in healthy male and female subjects.

Please refer to [section 8.3.1](#) (Source Documents) for the documentation requirements pertaining to the in- and exclusion criteria.

3.3.2 Inclusion criteria

1. Age between 18 and 65 years (inclusive)
2. BMI of >17.5 to <35.0 kg/m²
3. Healthy male or female subjects, according to the investigator's assessment, based on a complete medical history including a physical examination, vital signs (blood pressure [BP], pulse rate [PR]), 12-lead ECG, and clinical laboratory tests.
4. Subjects who meet any of the following criteria:
 - Surgically sterilized (confirmed 6 month prior to enrollment)
 - Have surgically sterilized sexual partner (confirmed 6 month prior to enrollment)

Boehringer Ingelheim
BI Trial No.: 1297.13
c11534380-01

23 Aug 2016

Trial Protocol

Page 20 of 58

Proprietary confidential information © 2016 Boehringer Ingelheim International GmbH or one or more of its affiliated companies

- Postmenopausal, defined as at least 1 year of spontaneous amenorrhea (in questionable cases a blood sample with simultaneous levels of FSH above 40 U/L and estradiol below 30 ng/L is confirmatory)
- 5. Subjects agree to use an adequate contraception, starting from the begin of the trial and until 6 months after the dose of the trial drug: e.g. any of the following methods plus condom: implants, injectables, combined oral or vaginal contraceptives, intrauterine device
- 6. Signed and dated written informed consent in accordance with GCP and local legislation prior to admission to the trial

3.3.3 Exclusion criteria

1. Previous exposure to adalimumab or proposed adalimumab biosimilar drugs.
2. Any finding in the medical examination (including BP, PR or ECG) that deviates from normal and judged as clinically relevant by the investigator.
3. Any evidence of a concomitant disease judged as clinically relevant by the investigator including gastrointestinal, hepatic, renal, respiratory, cardiovascular, metabolic, immunological, hormonal disorders or diseases of the central nervous system (including but not limited to any kind of seizures or stroke), and other relevant neurological or psychiatric disorders.
4. History of relevant orthostatic hypotension, fainting spells, or blackouts.
5. Chronic or relevant acute infections.
6. Positive result for HIV, HBV, and hepatitis C (Hep C) at screening.
7. History of relevant allergy or hypersensitivity including allergy to the trial medication, its excipients or device materials (e.g. natural rubber or latex).
8. Within 10 days prior to administration of trial medication, use of drugs that might reasonably influence the results of the trial.
9. Intake of an investigational drug in another trial within 2 months or 5 half-lives (whichever longer) prior to planned administration of the trial medication in this trial or intake of an investigational drug during the course of this trial.
10. Alcohol abuse (consumption of more than 28 units/week).
11. Unwillingness/inability to refrain from intake of alcoholic beverages from 48 hours prior to the trial medication administration and until Day 14 post trial medication administration; and/or to limit alcohol intake to a maximum of 3 units per day until e.o.t.
12. Drug abuse or positive drug screening.
13. Blood donation of more than 500 mL within 30 days prior to administration of trial medication or intended donation during the trial.
14. Intention to perform excessive physical activities within 4days prior to administration of trial medication or contact sport during the entire trial and unwilling to avoid vigorous exercise for 14 days post dosing.
15. Inability to comply with dietary regimen of trial site.
16. Any out-of-range laboratory values considered clinically significant by the investigator; (subjects with creatine kinase (CK) values 2 times the upper limit of normal (ULN) at Day -1 are to be) excluded from participation).

Boehringer Ingelheim
BI Trial No.: 1297.13
c11534380-01

23 Aug 2016

Trial Protocol

Page 21 of 58

Proprietary confidential information © 2016 Boehringer Ingelheim International GmbH or one or more of its affiliated companies

17. Subject is assessed as unsuitable for inclusion by the investigator, for instance, because he is considered not able to understand and comply with trial requirements, or has a condition that would not allow safe participation in the trial.
18. Subjects with any immunological disorders or auto-immune disorders, (e.g., RA, lupus erythematosus, scleroderma, etc.).
19. Subject has received a live vaccine within 12 weeks prior to enrolling in the trial.
20. History of TB or positive finding in IGRA.
21. Evidence of skin irritation or infection at the planned injection place.
22. Currently enrolled in another investigational device or drug study
23. Any condition that, in the investigator's opinion, makes them an unreliable study subject or unlikely to complete the trial
24. Women who are pregnant, nursing, or who plan to become pregnant while in the trial

3.3.4 Removal of subjects from therapy or assessments

3.3.4.1 Removal of individual subjects

An excessive withdrawal rate can have a severe negative impact on the scientific value of the trial. Every effort should be made to keep subjects in the trial as scheduled. This includes careful subject selection and appropriate explanation of the trial requirements and procedures prior to enrolment.

An individual subject is to be withdrawn from trial if:

- The subject withdraws consent for trial participation, without the need to justify the decision. In this case, no more assessments/investigations will be performed.
- The subject needs to take concomitant drugs that interfere with the investigational product
- The subject can no longer participate for other medical reasons (such as surgery, adverse events, other diseases, or pregnancy)
- The subject has repeatedly shown to be non-compliant with important trial procedures and, in the opinion of both, the investigator and sponsor representative, is not willing or able to stick to the trial requirements in the future.

Given the subject's agreement, the subject will undergo the procedures for early treatment discontinuation and follow up as outlined in the [Flow Chart](#) (FC) and [section 6.2.3](#).

For all subjects, the reason for withdrawal (e.g. adverse events) must be recorded in the CRF. These data will be included in the trial database and reported.

3.3.4.2 Discontinuation of the trial by the sponsor

Boehringer Ingelheim reserves the right to discontinue the trial overall or at a particular trial site at any time for the reasons including but not restricted to:

1. Failure to meet expected enrolment goals overall or at a particular trial site
2. Emergence of any efficacy/safety information invalidating the earlier positive benefit-risk-assessment that could significantly affect the continuation of the trial
3. Violation of GCP, the CTP, or the contract disturbing the appropriate conduct of the trial

Boehringer Ingelheim
BI Trial No.: 1297.13
c11534380-01

23 Aug 2016

Trial Protocol

Page 22 of 58

Proprietary confidential information © 2016 Boehringer Ingelheim International GmbH or one or more of its affiliated companies

In case the planned number of subjects cannot be randomized, the trial clinical monitor together with the trial pharmacokineticist and the trial statistician are to decide if the available sample size is sufficient to complete the trial.

The Investigator / the trial site will be reimbursed for reasonable expenses incurred in case of trial termination (except in case of the third reason).

3.3.5 Replacement of subjects

In case some subjects do not complete the trial, the trial clinical monitor together with the trial pharmacokineticist and the trial statistician are to decide if and how many subjects will be replaced. A replacement subject will be assigned a unique trial subject number, and will be assigned to the same treatment as the subject he replaces.

Boehringer Ingelheim
BI Trial No.: 1297.13
c11534380-01

23 Aug 2016

Trial Protocol

Page 23 of 58

Proprietary confidential information © 2016 Boehringer Ingelheim International GmbH or one or more of its affiliated companies

4. TREATMENTS

4.1 INVESTIGATIONAL TREATMENTS

The investigational products have been manufactured and will be provided by BI Pharma GmbH & Co. KG.

4.1.1 Identity of the Investigational Medicinal Products

The characteristics of the test products are given below:

Substance: BI 695501
Pharmaceutical formulation: Solution for injection in autoinjector
Source: BI Pharma GmbH & Co. KG, Germany
Unit strength: 40 mg / 0.8 mL
Posology: 1-0-0*
Route of administration: s.c.
Duration of use: single dose

Substance: BI 695501
Pharmaceutical formulation: Solution for injection in prefilled syringe
Source: BI Pharma GmbH & Co. KG, Germany
Unit strength: 40 mg / 0.8 mL
Posology: 1-0-0*
Route of administration: s.c.
Duration of use: single dose

*administered in the morning

BI 695501 autoinjector will be provided as sterile, preservative-free, non-pyrogenic, single-use prefilled syringes in autoinjectors containing 40 mg of BI 695501 per 0.8 mL. One autoinjector will be used per injection. The needle cap of the autoinjector syringe contains dry, natural rubber. BI is the final manufacturer of the BI 695501 autoinjector.

BI 695501 prefilled syringe will be provided as sterile, preservative-free, non-pyrogenic, single-use prefilled glass syringes containing 40 mg of BI 695501 per 0.8 mL. One syringe will be used per injection. The needle cap of the syringe contains dry, natural rubber.

Any unused product or waste material will be disposed of in accordance with local requirements.

4.1.2 Selection of doses in the trial

The dose selected for this trial reflects the standard clinical dose, and established similarity to the originator compound (see [Section 1.2](#)). The design and handling of the BI 695501 prefilled syringe and autoinjector do not significantly differ from the originator products as well and both presentations are intended to be marketed.

4.1.3 Method of assigning subjects to treatment groups

Prior to the screening visit, subjects will be contacted and informed about the planned visit dates.

Once subjects have completed screening, have met all the inclusion criteria and none of the exclusion criteria, randomization can occur prior to the planned dosing on Day 1. Subjects will be stratified by weight and site, and randomized sequentially.

Each prefilled syringe and autoinjector of the trial medication will be labeled with the trial code and a unique medication identification number.

The randomisation procedure is described in [Section 7.6](#).

4.1.4 Drug assignment and administration of doses for each subject

This is a single dose trial. All subjects will receive one of two possible treatments in a randomized order. The treatments to be evaluated are outlined in [Table 4.1.4: 1](#) below.

Table 4.1.4: 1 Dosage and treatment schedule

Treatment	Substance	Formulation	Unit strength	Dosage	Total dose
A	BI 695501	Solution for injection in autoinjector	40 mg	0.8 mL	40 mg
B	BI 695501	Solution for injection in prefilled syringe	40 mg	0.8 mL	40 mg

The autoinjector and prefilled syringe should be removed from refrigeration approximately 30 minutes before administration, to permit the medication to warm. Injecting cold medication can cause discomfort.

Boehringer Ingelheim
BI Trial No.: 1297.13
c11534380-01

23 Aug 2016

Trial Protocol

Page 25 of 58

Proprietary confidential information © 2016 Boehringer Ingelheim International GmbH or one or more of its affiliated companies

Trial medication will be administered as a single, s.c. injection while the subject is in a supine position by the trained investigator or designee. The time, injection location, and any difficulties with injection of the trial medication administration will be recorded in the eCRF. The location for the injection is the front of the thigh. Detailed “Instructions for use” for autoinjector and prefilled syringe will be provided in the ISF. Subjects will be kept under close medical surveillance until 24 hours following trial medication administration.

Standardized meals will be served during the residential period.

For restrictions with regard to diet see [Section 4.2.2.2](#).

4.1.5 Blinding and procedures for unblinding

4.1.5.1 Blinding

No blinding will be performed because the treatments are distinguishable from each other. This Phase I trial will be handled in an open-label fashion throughout (that is, during the conduct, including data cleaning and preparation of the analysis). This is considered acceptable because the potential for bias is low and does not outweigh practical considerations.

Emergency envelopes will not be provided, since all subjects will receive the same dose of the same drug via different presentations in an open-label design.

PK samples will be labelled in such a way that treatment allocation cannot be derived by the analytical site and the bioanalyst will remain blinded.

4.1.5.2 Unblinding and breaking the code

Not applicable.

4.1.6 Packaging, labelling, and re-supply

The investigational products will be provided by BI. They will be packaged and labelled in accordance with the principles of Good Manufacturing Practice (GMP). For details of packaging, retention sampling, and description of the labels refer to the ISF. Re-supply of the trial medication may occur on an as-needed basis during the trial.

4.1.7 Storage conditions

Drug supplies will be kept in their original packaging and in a secure limited access storage area according to the labelled storage conditions. The medication must be stored in a refrigerator at a controlled temperature (2 to 8°C [36 to 46°F]) and must not be frozen. A

Boehringer Ingelheim
BI Trial No.: 1297.13
c11534380-01

23 Aug 2016

Trial Protocol

Page 26 of 58

Proprietary confidential information © 2016 Boehringer Ingelheim International GmbH or one or more of its affiliated companies

temperature log must be maintained to make certain that the drug supplies are stored at the correct temperature. If the storage conditions are found to be outside the specified range, the Clinical Research Associate (CRA) (as provided in the list of contacts) is to be immediately contacted.

4.1.8 Drug accountability

The Investigator < and/or > Pharmacist < and/or > investigational drug storage manager will receive the investigational drugs delivered by the sponsor when the following requirements are fulfilled:

- Approval of the trial protocol by the IRB / ethics committee Institutional Review Board (IRB) / Independent Ethics Committee (IEC)
- Availability of a signed and dated clinical trial contract between the sponsor and the head of the investigational site,
- Approval/notification of the regulatory authority, e.g. competent authority,
- Availability of the curriculum vitae of the principal Investigator,
- Availability of a signed and dated clinical trial protocol
- Availability of the proof of a medical license for the principal Investigator
- Availability of Form 1572, if applicable

Only authorized personnel as documented in the form ‘Trial Staff List’ (site delegation log) may dispense medication to trial subjects. The identification of drug kits for retention sampling must be completed by the designated site personnel.

The trial medication must be administered in the manner specified in the CTP. All unused medication will be disposed locally by the trial site upon written authorization by the clinical monitor. Receipt, usage and disposal must be documented on the respective forms. Account must be given for any discrepancies.

The investigator must maintain records of the product’s delivery to the trial site, the inventory at the site, the use by each subject, and the disposal of unused products.

These records will include dates, quantities, batch / serial numbers, expiry (‘use-by’) dates, and the unique code numbers assigned to the investigational products and trial subjects. The investigator will maintain records that document adequately that the subjects were provided the doses specified by the CTP, and that reconcile all investigational products received from the sponsor. At the time of disposal, the investigator must verify that all unused or partially used drug supplies have been returned and that no remaining supplies are in the investigator’s possession.

Boehringer Ingelheim
BI Trial No.: 1297.13
c11534380-01

23 Aug 2016

Trial Protocol

Page 27 of 58

Proprietary confidential information © 2016 Boehringer Ingelheim International GmbH or one or more of its affiliated companies

4.2 OTHER TREATMENTS, EMERGENCY PROCEDURES, RESTRICTIONS

4.2.1 Other treatments and emergency procedures

There are no specific rescue drugs foreseen for the treatment of AEs. No special emergency procedures are to be followed. No additional treatment is planned. However, in case of AEs in need of treatment, the investigator can authorize symptomatic therapy. In those cases, subjects will be treated as necessary and, if required, kept under supervision at the trial site or transferred to a hospital until all medical evaluation results have returned to an acceptable level.

4.2.2 Restrictions

4.2.2.1 Restrictions regarding concomitant treatment

In principle, no concomitant therapy is expected in this healthy volunteers trail. All concomitant or rescue therapies will be recorded (including time of intake on trial days) on the appropriate pages of the eCRF. Hormonal contraceptives are allowed for women of child-bearing potential; limited amounts of paracetamol (or ibuprofen) are allowed to treat aches and pains.

Supplements and herbal preparations are discouraged from use during the course of the trial. Vitamins may be used during the trial based on the discretion of the investigator.

Any live or attenuated vaccines are strictly prohibited during the course of the trial. Use of any prescribed or over-the counter drugs should be reported and discussed with the investigator.

The subjects are instructed not to undergo any medical treatment or any surgical procedure 14 days prior to, during and until the end of the trial without having informed the investigator or his deputy unless necessary to treat medical emergencies.

4.2.2.2 Restrictions on diet and life style

While admitted to the trial site the subjects are restricted from smoking, consuming any food or drink other than those provided by the site staff.

On all days when laboratory sampling is planned, subjects must have fasted for 4 hours prior to blood samples being collected.

Excessive exercise should be avoided from 4 days prior to and up to 14 days after trial medication administration. Contact sport must be avoided for the duration of the trial.

Female subjects and Male subjects with female partner(s) of child-bearing potential must agree to use a medically acceptable method of contraception during the trial and for 6 months after the dose of trial drug. Males and male partners of female subjects should use a condom.

Boehringer Ingelheim
BI Trial No.: 1297.13
c11534380-01

23 Aug 2016

Trial Protocol

Page 28 of 58

Proprietary confidential information © 2016 Boehringer Ingelheim International GmbH or one or more of its affiliated companies

Female subjects and female partners of male subjects must additionally use one of the following methods if they are not pregnant: implants, injectables, combined oral or vaginal contraceptives, intrauterine device.

Male subjects must also agree to not donate sperm during the trial and for a period of 6 months after the last dose of trial drug.

Subjects should abstain from alcoholic beverages for 24 hours prior to each trial visit. Alcoholic beverages are not permitted from 48 hours prior to the first trial medication administration on Day 1 and until Day 14 and then no more than three units of alcohol per day are allowed until e.o.t.

One unit of alcohol is 10 mL (1 cL) by volume, or 8 g by weight, of pure alcohol. For example:

One unit of alcohol is about equal to:

- Half a pint (290 mL) of ordinary strength beer, lager, or cider (3% to 4% alcohol by volume); or
- A small pub measure (25 mL) of spirits (40% alcohol by volume): or
- A standard pub measure (50 mL) of fortified wine such as sherry or port (20% alcohol by volume).

There are one and a half units of alcohol in:

- A small glass (125 mL) of ordinary strength wine (12% alcohol by volume); or
- A standard pub measure (35 mL) of spirits (40% alcohol by volume).

4.2.2.3 Restrictions regarding women of childbearing potential

A serum beta-human Chorionic Gonadotropin (β -hCG) test will be performed at Screening in women of childbearing potential. A local urine pregnancy test will be then performed as indicated in the [Flow Chart](#). Any woman with a confirmed positive pregnancy test during screening is not eligible for the trial. A positive urine pregnancy test during the study duration should be reported and followed up. Female subjects of childbearing potential must use the contraception methods described in [Section 4.2.2.2](#) and the subject information.

Acceptable methods of birth control include, for example, birth control pills, intrauterine devices (IUDs), surgical sterilization, vasectomized partner and for example male condom in combination with female implants, injectables, combined oral or vaginal contraceptives, intrauterine device).

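### Protocol 4.2.2.3 binds women of childbearing potential to the contraception in 4.2.2.2, then lists pills and IUDs without a condom as acceptable, which does not match 4.2.2.2 or inclusion criterion 5

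*Protocol*

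**What the plan says.** Three places in the protocol describe contraception for women of childbearing potential.

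- **3.3.2, inclusion criterion 5.** Subjects agree to adequate contraception from the beginning of the trial until 6 months after the dose, illustrated by "e.g. any of the following methods plus condom: implants, injectables, combined oral or vaginal contraceptives, intrauterine device".
- **4.2.2.2, under diet and life style.** "Males and male partners of female subjects should use a condom". The second element is for the women concerned, whether they are in the trial themselves or are partners of men who are. The wording for them is "must additionally use one of the following methods if they are not pregnant: implants, injectables, combined oral or vaginal contraceptives, intrauterine device".
- **4.2.2.3, on women of childbearing potential.** A binding sentence comes first: "Female subjects of childbearing potential must use the contraception methods described in", with a pointer to 4.2.2.2 and to the subject information. A list follows directly: "Acceptable methods of birth control include, for example, birth control pills, intrauterine devices (IUDs), surgical sterilization, vasectomized partner", and the same sentence goes on "and for example male condom in combination with female implants, injectables, combined oral or vaginal contraceptives, intrauterine device".

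The protocol does not say which of the three prevails if they differ.

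**The concern.** Oral contraceptives and IUDs appear without a condom in one place and with one in the two others. Section 4.2.2.3 is also at odds with itself: the sentence that points to 4.2.2.2 is followed at once by a list that does not match what 4.2.2.2 describes.

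The rule is part of eligibility (criterion 5) and of the restrictions during the trial. Section 4.3 allows subjects who break trial restrictions to be removed, so staff need to know what counts as a breach. The purpose is to avoid fetal exposure: pregnancy is an exclusion criterion, and 5.3.7.2 requires potential exposure to be reported within 24 hours. The obligation lasts until 6 months after the dose, while the last planned contact is on Day 70. What the woman is told at enrolment therefore has to cover a long stretch without further visits.

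**Working it through.** No arithmetic decides this point. The check is to compare the three texts and then apply each to the same woman.

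**Step 1: content and force of each text**

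| Place | Condom | Female method | Force |
|---|---|---|---|
| Criterion 5 | Together with the female method | Implant, injectable, combined oral or vaginal contraceptive, IUD | Adequate contraception is the condition; the combination is an example ('e.g.') |
| 4.2.2.2 | Yes | Same four groups | Condom 'should'; female method 'must additionally' |
| 4.2.2.3, binding sentence | As in 4.2.2.2 | As in 4.2.2.2 | 'must' |
| 4.2.2.3, list, first items | None stated | Pills, IUD (also sterilization, vasectomized partner) | 'acceptable', as examples |
| 4.2.2.3, list, last item | Yes | Same four groups | 'acceptable', as an example |

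**Step 2: can the first items of the list be read as including a condom?** Hardly. Surgical sterilization and a vasectomized partner stand in the same series and are plainly complete in themselves. Oral contraceptives and IUDs are then named a second time in the condom combination. That repetition makes sense only if the first mention is without a condom.

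**Step 3: apply the texts** (taking the pill to be a combined oral contraceptive)

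| Woman of childbearing potential uses | 4.2.2.3 list | 4.2.2.2 | Criterion 5 |
|---|---|---|---|
| Pill or IUD with condom | Fits | Fits | Matches the example |
| Pill or IUD alone | Fits | The 'must' is met, the 'should' is not | Does not match the example; whether it is still adequate is left open |

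The second row is the inconsistency. Sterilization and a vasectomized partner are left out of it, because inclusion criterion 4 deals separately with sterilization of the subject or the partner.

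**Step 4: can the group be counted?** Sections 3.1 and 7.6 fix only the background: 160 subjects, at least 30% of each gender, two sites. That gives at least 0.30 × 160 = 48 women and at most 160 − 48 = 112. The affected group is the part of these who are of childbearing potential and use a pill or IUD without a condom. Neither proportion is stated, so the number cannot be derived.

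**The case against.** The best defence is that the governing rule is stated. The only 'must' on contraception in 4.2.2.3 sends the reader to 4.2.2.2, while the list after it is introduced as examples and has no binding verb. A site that follows the binding sentence applies 4.2.2.2, and the list is merely loose. This has weight and limits the point. It does not remove it: the list calls these methods acceptable immediately after the cross-reference, no precedence is given, and 4.2.2.3 is the section headed for these women, whereas 4.2.2.2 is headed for diet and life style.

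Four further objections:

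- **The condom is not strictly mandatory.** A reader might infer that criterion 5 and 4.2.2.2 require a condom, so that a woman on a pill or IUD alone fails both. The documents do not go that far, given 'e.g.' in one and 'should' in the other. Still, 'additionally' shows that 4.2.2.2 has two methods in mind.
- **Different enrolment at the two sites is not shown.** A reader might infer that the sites would enrol different women. Criterion 5 is an agreement, so a woman on a pill or IUD can satisfy the stricter reading by agreeing to add a condom. Only one who declines would be treated differently.
- **Part of the text cannot be checked.** The subject information is not among the documents and may already state one rule. The list sentence also ends with a closing bracket that has no opening one; whether this comes from drafting or from text extraction is unknown. The repetition in step 2 does not depend on that bracket.
- **Few such women may enter.** Criterion 4, read literally, could suggest this. But 4.2.2.1 allows them hormonal contraceptives, Table 5.3.3:1 schedules pregnancy tests for them, and SAP section 10 tabulates childbearing potential. The plan expects them.

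**Conclusion.** The inconsistency is real and confined to wording. A woman using a pill or IUD alone is within the 4.2.2.3 list and outside the two-method arrangement that 4.2.2.2 describes and criterion 5 illustrates. Counselling at enrolment, and any later judgement of compliance, could therefore differ with the section consulted.

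The size of the affected group is unknown. The minimum of 48 women might be taken for it, but that figure includes postmenopausal and sterilized women and says nothing about contraceptive practice.

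There is no effect on sample size, power or the PK analysis. Exclusion from the PK analysis set (protocol 7.3.1, SAP 5.6) turns on deviations thought to affect the PK of BI 695501, and nothing in the documents connects condom use with that.

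The conclusion assumes that the list sentence in 4.2.2.3 is reproduced as drafted apart from its punctuation. It takes no position on which contraception rule is clinically right.

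**What to change.** Reconcile inclusion criterion 5, 4.2.2.2 and 4.2.2.3 so that all three state the same rule with the same force, using 'must', 'should' or 'e.g.' alike in each. One way is to state the rule once and have the other two places refer to it without a list of their own. Check the subject information against the result. The responsible clinicians decide which rule applies.

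The cost is wording, together with the approval that 8.1 requires before an amendment is implemented. No procedure, sample size or analysis changes.
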